4.8. Unique Study Identification Code

Each subject will be assigned a unique study identification code in an effort to protect subject confidential information. The unique study identity code will be pseudonymized and will not include date of birth or subject's first and last initials and will be used to link study data and other study information to the subject in lieu of the subject name. The Subject Name Log will be used to link the unique study identity code to the subject and will be maintained at each site. This log will remain confidential and will not be provided to the Sponsor, but only used for reference when monitoring at the study site.

4.9. Subject Recruitment

Subjects who present with resistant hypertension consistent with the 2018 ESC/ESH Guidelines for the management of arterial hypertension will be considered potential study candidates. The Sponsor does not intend to advertise or otherwise actively recruit subjects.

4.10. Subject Reimbursement

Subjects will not be reimbursed or compensated for participating in the trial. Reasonable travel costs associated with follow-up visits may be reimbursed upon request.

4.11. Enrollment

Patient eligibility will be confirmed prior to insertion of the investigational device, and subjects will be considered enrolled in the study at the time that the skin is broken to implant the baroloop System.

Subjects who sign consent but are excluded before enrollment will not be included in the primary analysis of the study endpoints. The reason for exclusion will be documented in the Consent and Screening Log and the consent document maintained in the site's study records.

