4.2. Primary Study Endpoints

4.2.1. Safety

Composite Major Adverse Event (MAE) Rate at six (6) months post-treatment including:

- All-causes of death
- Hospitalization for hypertensive crisis post-titration
- Any device or procedure-related serious adverse event

All MAEs will be adjudicated by an independent Data Safety Management Board (DSMB).

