4.14. Withdrawal of Subjects

Each subject may voluntarily withdraw his / her participation from the study at any time. Investigators may discontinue a subject's participation in the study as deemed appropriate for safety considerations and / or if the subject's medical condition contraindicates further study participation. All enrolled subjects will undergo the complete study follow-up for safety evaluation.

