5.3. Potential Adverse Events

Surgery-related

- hematoma
- infection
- pain
- voice alteration (hoarseness)

Stimulation-related

- bradycardia
- dyspepsia (indigestion)
- dysphagia (difficulty swallowing)
- dyspnea (difficulty breathing, shortness of breath)
- hypotension
- increased coughing
- laryngismus (throat, larynx spasms)
- pain
- paresthesias (prickling of the skin)
- pharyngitis (inflammation of the pharynx, throat)
- satiety (reduced appetite)
- sensation of stimulation
- syncope
- voice alteration (hoarseness)

It is anticipated that subjects will be exposed to operative and post-operative risks similar to related surgical procedures involving the neck and/or a pacemaker implant. These risks and potential risks of chronic device based baroreflex activation may include, but are not limited to:

- Surgical or anesthetic complications
- Infection – the need for antibiotics or possible removal of the system
- Wound Complication –including hematoma (i.e. bruising and/or swelling)
- Arterial damage –including carotid artery rupture or hemorrhage (sudden and significant blood loss at a site of blood vessel rupture that may require reoperation or transfusion)
- Pain – an unpleasant sensory experience
- Nerve Damage/Stimulation –including injury to or stimulation of Cranial, Marginal Mandibular, Glossopharyngeal, Recurrent Laryngeal, Vagus and Hypoglossal Nerves (numbness in head and neck, facial palsy/paralysis, altered speech, altered sense of taste, respiratory constriction, stertorous breathing, excessive salivation, dry cough, vomiting and/or regurgitation, altered sensory and motor function of tongue, altered sensory function of pharynx and oropharynx, altered sensation in external auditory canal), stimulation of extravascular tissue (muscle twitching (fasciculation), pain, tingling, oral sensations)
- Hypotension – a decrease in systolic and diastolic blood pressure below normal levels that may result in dizziness, fainting, and/or falls
- Hypertensive crisis – uncontrolled rise in blood pressure
- Respiratory – including low oxygen saturation, respiratory distress, shortness of breath
- Exacerbation of heart failure

 neuroloop	Confidential	Protocol – The baroloop Study
--	---------------------	-------------------------------------

- Cardiac arrhythmias
- Tissue erosion/IPG migration – movement of device resulting in need for reoperation

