6.1. Overview

The primary objective of this study is to characterize the safety and feasibility of the baroloop System in subjects with uncontrolled or resistant hypertension. All subjects will be followed on an intent-to-treat basis (ITT). The device performance will also be assessed based on a per-protocol analysis of the primary safety and feasibility endpoints and secondary efficacy endpoints. An intent-to-treat analysis, along with other secondary analyses, will also be completed and reported.

This is not a hypothesis driven study, and no formal power analysis or hypothesis-driven statistical analysis has or will be performed. Standard summary statistics will be calculated for all study variables. For continuous variables, statistics will include means, standard deviations, medians and ranges. Categorical variables will be summarized using frequency distributions.

The primary endpoints will be analyzed on an intent-to-treat (ITT) basis, for which data from all subjects enrolled will be included. In order to evaluate a true treatment effect, the primary analysis will include those subjects achieving technical success, the definition of which includes successful completion of the study procedure.

If there are no more than 4 failures to implant, combined with a safety level that is determined by the independent DSMB to be acceptable, together with any reduction in blood pressure as a result of the baroloop therapy, this will be considered a successful outcome to this First-in-Human study.

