An overreaction of the body's immune system to a component of an investigational device (e.g., nitinol metal, polyester, plastics), contrast agents and / or anesthesia medication given to the subject for completion of a study related procedure (e.g., MSCT, angiogram, investigational device), which requires medical intervention to treat the allergic reaction.

Acute Kidney Injury (AKI)

- Stage 1: Increase in serum creatinine to 150–199% (1.5– 1.99 × increase compared with baseline) OR increase of ≥ 0.3 mg / dL (≥ 26.4 μ mol / L) OR Urine output <0.5 ml / kg per hour for >6 but <12 hours
- Stage 2: Increase in serum creatinine to 200–299% (2.0– 2.99 × increase compared with baseline) OR Urine output <0.5 ml / kg per hour for >12 but <24 hours
- Stage 3: Increase in serum creatinine to $\geq 300\%$ (>3 × increase compared with baseline) OR serum creatinine of ≥ 4.0 mg / dL (≥ 354 mmol / L) with an acute increase of at least 0.5 mg / dL (44 mmol / L) OR Urine output <0.3 ml / kg per hour for ≥ 24 hours OR Anuria for ≥ 12 hours [Subjects receiving renal replacement therapy are considered to meet Stage 3 criteria irrespective of other criteria]

AV Block

Atrioventricular block is a type of heart block in which the conduction between the atria and ventricles of the heart is impaired.

Blood Loss

- Major Blood Loss – Defined as transfusion of >2 units packed red blood cells (PRBC)).
- Estimated Procedural Blood Loss – Defined as the total estimated blood loss (mL) during the index procedure. Includes blood loss resulting from adjunctive procedures performed during the index-procedure.

Bleeding

- Life-threatening or disabling bleeding:
 - Fatal bleeding (BARC type 5) OR
 - Bleeding in a critical organ, such as intracranial, intraspinal, intraocular, or pericardial necessitating pericardiocentesis, or intramuscular with compartment syndrome (BARC type 3b and 3c) OR
 - Bleeding causing hypovolemic shock or severe hypotension requiring vasopressors or surgery (BARC type 3b) OR
 - Overt source of bleeding with drop in hemoglobin of ≥ 5 g / dL or whole blood or packed red blood cells (RBCs) transfusion ≥ 4 units* (BARC type 3b)
 - Given one unit of packed RBC typically will raise blood hemoglobin concentration by 1 g / dL, an estimated decrease in hemoglobin will be calculated; BARC: Bleeding Academic Research Consortium.

 neuroloop	Confidential	Protocol – The baroloop Study
--	---------------------	-------------------------------------

- Major bleeding:

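### A death or procedure-related serious event under anaesthesia that stops the operation before the incision is left out of the primary MAE rate

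*Combined protocol and SAP*

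**What the plan says.** Section 4.11 sets the time of enrolment: "subjects will be considered enrolled in the study at the time that the skin is broken to implant the baroloop System". It then deals with those who do not get that far: "Subjects who sign consent but are excluded before enrollment will not be included in the primary analysis of the study endpoints".

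Section 6.1 gives two sets for the primary endpoints. One is the intention-to-treat set: "The primary endpoints will be analyzed on an intent-to-treat (ITT) basis, for which data from all subjects enrolled will be included". The next sentence gives a narrower one: "the primary analysis will include those subjects achieving technical success".

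The primary safety endpoint in section 4.2.1 is a composite MAE rate at six months after treatment. It counts death from any cause, hospitalisation for hypertensive crisis after titration, and "Any device or procedure-related serious adverse event". No start of the event window is given.

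On anaesthesia, section 5.3 lists "Surgical or anesthetic complications" among the operative risks. The allergic-reaction entry in section 12 refers to "anesthesia medication given to the subject for completion of a study related procedure". The procedure-time entry in section 12, however, starts the clock at the initial skin incision.

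**The concern.** In a first-in-human implant study, safety is a primary objective and the MAE rate is its headline figure. Exposure to the risks of the operation begins when anaesthesia is started, but the population for the headline figure begins at the incision. A subject can therefore be exposed to a study-required intervention, be harmed by it, and leave the primary population because of that harm.

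For subjects who fail eligibility, the exclusion in 4.11 is an ordinary screen-failure rule. For a case abandoned after induction because of a serious event, exclusion depends on the outcome. Leaving out such a case can only lower the reported rate. With at most 10 subjects, one case moves that rate visibly.

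**Working it through.** **Inputs.** Enrolment point and exclusion: 4.11. Analysis sets: 6.1. MAE components: 4.2.1. Sample size, up to 10 enrolled: 4.4. Adverse events are marked from Visit 1 in Table 3 and reviewed on the day of implantation (4.21). The plan has no sample-size or power figure to reproduce, because 6.1 disclaims a formal power analysis.

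**Step 1: which cases are lost.** Take a serious event after induction and before the incision.

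| Course | Enrolled (4.11)? | In ITT set (6.1)? | In technical-success set (6.1)? | Can count as MAE? |
|---|---|---|---|---|
| Incision follows | Yes | Yes | Only if technical success is reached | Yes, under ITT |
| Operation abandoned before incision | No | No | No | No |

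In the first row the event can count because all data of enrolled subjects are included and the MAE definition has no lower time limit. Only the second row is lost.

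**Step 2: does the event meet the MAE definition?** Death from any cause does, with no test of relatedness. A non-fatal serious event does if anaesthesia is part of the procedure. Section 5.3 points that way and the procedure-time entry in section 12 points the other way. The documents do not settle it.

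**Step 3: effect on the rate.** Rate = x/n with exact (Clopper-Pearson) 95% limits. Suppose 10 subjects are enrolled and one further subject is abandoned because of such an event.

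| Other MAEs | As written | Counted from start of anaesthesia | Shift (points) |
|---|---|---|---|
| 0 | 0/10 = 0% (0 to 30.8%) | 1/11 = 9.1% (0.2 to 41.3%) | 9.1 |
| 1 | 1/10 = 10.0% (0.3 to 44.5%) | 2/11 = 18.2% (2.3 to 51.8%) | 8.2 |
| 2 | 2/10 = 20.0% (2.5 to 55.6%) | 3/11 = 27.3% (6.0 to 61.0%) | 7.3 |

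If the place is not refilled and 9 are enrolled, 0/9 = 0% (0 to 33.6%) becomes 1/10 = 10.0% (0.3 to 44.5%).

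**Step 4: how likely is it?** The documents give no rate, so p, the per-subject risk of a serious event that also leads to abandonment before the incision, is an assumption. Among 11 subjects taken to theatre, P(at least one) = 1 − (1 − p)^11. This gives 1.1% for p = 0.1%, 5.4% for p = 0.5% and 10.5% for p = 1%.

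**The case against.** The strongest reply is that nothing is hidden. Serious events are reported within 24 hours whatever their cause (7.2, 7.9). Section 7 sends all of them to the DSMB and says that the adjudicated results enter the data analysis, and events are followed until resolved. The early-termination rule in 9.13 and the success rule in 6.1 carry no numerical safety threshold: the DSMB judges, and it would know of the case. Section 5.5 also lets the Medical Monitor or DSMB recommend stopping enrolment over a safety issue. This stands. What is affected is the reported primary rate. Section 7 does not say which analysis set the adjudicated results enter, whereas 4.11 expressly keeps these subjects out of the primary one.

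A reader might also infer more than the documents support:

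- *That every serious event before the incision is lost.* It is not; if the incision follows, the subject is enrolled and the event can count.
- *That such a subject gets no safety follow-up, because 4.14 says "All enrolled subjects will undergo the complete study follow-up for safety evaluation".* That sentence promises the full schedule to enrolled subjects. Section 7 separately requires events to be followed to resolution and does not limit this to enrolled subjects.
- *That the place would be refilled.* The plan says up to 10 and has no replacement rule.
- *That the percentages in step 4 estimate the risk.* They rest wholly on an assumed p.

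It can also be said that anaesthesia is not the procedure, because section 12 times the procedure from the incision. That entry defines a duration only, and the allergic-reaction entry is weak evidence the other way, since it mentions imaging that is not in the visit schedule. The plan should state the answer. For death the question does not arise.

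**Conclusion.** The point holds for one kind of case: a death, or a serious event judged procedure-related, that occurs under anaesthesia and leads to abandonment before the incision. Such a case is in neither primary set of 6.1 and is missing from the MAE rate, though not from safety reporting or DSMB review.

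One case would move the observed rate by about 7 to 9 percentage points with 10 enrolled, for example from 0% to 9.1%. For the non-fatal case this assumes that anaesthesia counts as part of the procedure. The case is probably rare, and no frequency can be taken from the documents. No effect on a stopping or success decision can be shown, because those judgements have no numerical threshold. The change is worth making because the omission is tied to the harm itself and the correction is cheap.

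**What to change.** In 4.11 and 6.1:

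1. Define the analysis set for the primary and secondary MAE endpoints as every subject in whom anaesthesia for the baroloop implantation was started, whether or not the skin was broken.
2. Open the MAE event window at that time, and state that anaesthesia is part of the procedure when relatedness is judged.
3. State that this set, not the technical-success subset in 6.1, is used for the MAE rate. Without this the two sentences in 6.1 still conflict: a cancelled subject can never reach technical success, and MAEs in enrolled subjects with a failed implant could also be dropped.
4. Keep skin incision as the enrolment point for feasibility and for the limit of 10.
5. For subjects never incised, refer to the follow-up to resolution that section 7 already requires, not to the full visit schedule under 4.14.

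The cost is a few sentences. Adverse events are already collected from Visit 1 and serious events already go to the DSMB, so no new event collection is needed before the incision. The downside is that the MAE and feasibility denominators may differ by any cancelled cases, which the report should list. A cancelled case without an event would have shorter follow-up than the six-month window, and the listing should show this.

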4.12. Duration of Subject Participation

Subjects enrolled in the trial will participate for approximately 2 years and 2 months.

4.13. Study Duration

This study is expected to enroll up to 10 subjects within approximately 36 months. The closeout phase of the study is expected to be completed within 6 months following the last subject follow-up visit. The total duration of the study is estimated to be 5.5 years.

 neuroloop	Confidential	Protocol – The baroloop Study
--	---------------------	-------------------------------------

4.14. Withdrawal of Subjects

Each subject may voluntarily withdraw his / her participation from the study at any time. Investigators may discontinue a subject's participation in the study as deemed appropriate for safety considerations and / or if the subject's medical condition contraindicates further study participation. All enrolled subjects will undergo the complete study follow-up for safety evaluation.

4.15. Loss to Follow-up Considerations

A subject will be considered lost to follow-up and terminated from the study when all of the following criteria have been met:

- Documentation of three unsuccessful attempts on three different days over a period of three (3) months by the Investigator or his / her designee to contact the subject or next of kin, one of which should be by certified mail with signature confirmation.
- Prior agreement of the Sponsor to remove the subject from the clinical investigation.

If permitted by the subject in the informed consent, contact with the family doctor may be made only after three unsuccessful attempts have been made to contact the study subject.

[figure not shown]
[figure not shown]
4.16. Subject Confidentiality

All information concerning subjects or their participation in this trial will be considered confidential. Only authorized representatives, designated personnel of the CRO, designated consultants, or regulatory agencies will have access to these confidential files. Subject names or other non-pseudonymous data that could directly identify a patient will not be captured on the case report forms. In addition, all patient identifiers except the unique study identification code will be redacted from any X-ray, CT and MRI images submitted from the participating site to the Sponsor or the Sponsor's designated reviewers for analysis.

4.17. Study Procedures

4.17.1. Screening and Enrollment

The overall screening and enrollment scheme for the study is shown in schematic form in Figure 2 and identifies the various phases for screening, consenting, continued eligibility assessment and assignment into the subject cohorts for the study.

**Figure 2: baroloop Trial Screening and Enrollment Scheme**

4.17.2. Consent Phase

Prior to obtaining written informed consent, the subject's existing medical records may be reviewed by the site to determine whether or not the subject might be an acceptable candidate for this study.

If initial review of the medical records indicate that the subject may be eligible (i.e., the patient has uncontrolled or resistant hypertension as defined in the 2018 ESC/ESH Guidelines for the management of arterial hypertension), the informed consent process may commence.

 neuroloop	Confidential	Protocol – The baroloop Study
--	---------------------	-------------------------------------

4.17.3. Screening Phase

Each patient's medical records will be reviewed to assess compliance with the eligibility of the baroloop Study. Patients who are eligible based on the study enrollment criteria will proceed to the next phase of the study.

4.17.4. Eligibility Assessments

Baseline evaluation will be performed after the subject has provided written informed consent in order to ensure that the subject is an appropriate candidate for this study and to obtain baseline values for study endpoint evaluation.

If the subject continues to meet the study's enrollment criteria and continues to be willing and able to participate in the study protocol, the subject will be enrolled.

All subjects will undergo a series of baseline evaluations (if not already available as part of the existing medical records). Baseline visit and data collection can occur anytime within 6 months before the implantation procedure of the baroloop System (see Figure 2).

4.18. Procedural Treatment and Timing

4.18.1. Medication Regimen

All participants in the study will be on a minimum of three (3) anti-hypertensive drugs such as, but not limited to, a diuretic (usually a thiazide or loop diuretic), a calcium channel blocker and an angiotensin converting enzyme inhibitor. Patients may be on additional antihypertensive drugs such as alpha- or beta-blockers, direct acting vasodilators angiotensin receptor blockers or combinations of these drugs. Where possible, simpler (fewer drug) regimens are preferred. Regardless of the of the particular three or greater combination of drugs, every effort should be made to maintain each patient on a stable regimen of antihypertensive medicines during the course of the study.

4.19. Baseline Assessment: Visit 1

The following information will be assessed, and the documentation will be maintained as source records at the study site:

- Medical history;
- Office cuff blood pressure;
- Check for orthostatic blood pressure and orthostatic pulse assessments;
- Current medication history including all hypertensive medication;
- Physical examination;
- Laboratory testing;
- Quality of Life SF-36 questionnaire.

4.20. Baseline Assessment: Visit 2 (four weeks after visit 1)

- Office cuff blood pressure;

 neuroloop	Confidential	Protocol – The baroloop Study
--	---------------------	-------------------------------------

- Current medication history including all hypertensive medication including changes of medication regimen;
- Review and assessment of adverse events;
- 24 hour ambulatory blood pressure measurement (24hr ABPM) after observed therapy for hypertension.
- Medication compliance testing
- Quality of Life SF-36 questionnaire.

4.21. Day of Implantation procedure

- Physical examination;
- Changes of medication regimen;
- Review and assessment of adverse events;
- Office cuff blood pressure; and
- Assessment of all Inclusion/Exclusion criteria.

4.22. baroloop System Implantation Procedure

The implantation operation should be performed as described in the baroloop Implantation Manual (BL_IM_Implantation_Manual_FIH). In brief, the procedure should be performed using a neurosurgical microscope after the initial incision in the left side of the neck is made over the location of the vagus nerve (from point 3 on). A subcutaneous pocket (size 6 x 7 cm) should be created under the skin and over the pectoralis muscle below the left clavicle to house the IPG. To access the left vagal nerve, a horizontal cervical skin incision 4-5 cm in length on the left neck should be made between the clavicle and mandible. The tissue should be carefully dissected to expose the neurovascular sheath containing the vagus. The sheath should be opened to expose the left vagus nerve over a length of approximately 3 cm. A neuroloop Cuff size should be select that matches the approximate size of the vagal nerve diameter. Before placing the Cuff, the Pill should be fixed to the underlying tissue according to the instructions in the baroloop Implantation Manual. After fixing the Pill, the Cuff should be wrapped around the vagus nerve, and proper rim alignment of the Cuff edges should be reviewed to make sure that both ends of the cuff are square and perpendicular to the long axis of the cuff. Strain relief loops in the Cable leading to the IPG should be created using the suture sleeves. The Lead should be passed subcutaneously from the cervical incision site to the pectoral pocket where the IPG is placed. The Connector should be cautiously passed through tunnelling device to the subcutaneous pectoral pocket. After removing the Tunnelling device by pulling in pectoral direction, which was inserted from the pectoral pocket to the neck, the Connector to the IPG should be cleaned, if necessary, prior to connecting it to the IPG. The Connector should be fixed in the appropriate receiving slot in the IPG using the torque key. Perform initial device testing, described below, before closing the surgical incisions.

After the Cuff, Pill, Lead and IPG are connected, the device must be tested. Please see the Implantation Manual and Programmer Manual for complete details of testing. Briefly, an impedance test should be performed before the IPG is placed. If impedance test is 'Passed',

place the IPG in the prepared pectoral pocket. If impedance is 'Failed', follow the steps in flow chart in the Implantation Manual to obtain a 'Passed' impedance test. After the Impedance test is passed, place the IPG in the pectoral pocket with the neuroloop logo pointing to the skin surface. Perform a 2nd impedance test. If impedance 'Passed', follow the tests. If impedance 'Failed', follow steps in Implantation Manual flow chart to obtain a 'Passed' impedance test.

Once the impedance tests have been passed, both surgical sites should be irrigated with saline before closure of each surgical incision. Incision closure should be completed with sutures in layers, and a stapler must NOT be used to close the wounds!

After wound closure, a brief 'intraoperative' stimulation test must be performed to confirm proper functioning of the neuroloop device. Please consult the Programmer Manual and Implantation Manual for detailed instructions (BL_PM_Programmer_Manual_FIH and the BL_IM_Implantation_Manual_FIH). To begin, place the Charger within its sterile cover on the implanted IPG. Use the programmer to select 'Surgery Mode' and login into the Programmer. The Charger and the IPG will connect automatically, which will be reflected on the Programmer screen. Once the 'Surgery Mode' screen appears, press the 'START STIMULATION TEST' button on the Programmer screen. The electrode that is currently being tested will be highlighted. The stimulation or pause time is displayed. The stimulation time for each electrode is 30 seconds, and the pause time between two stimulations is 30 seconds. The overall test time, if all electrodes are functional, will be 12 minutes. Once the test is finished, completion of the test is displayed in the Programmer screen. The data from the intraoperative testing may be downloaded for analysis by neuroloop.

Please note that intra-operative testing is done to confirm that the device is properly connected, that the batteries effectively drive and control the device, and that the device contacts the proper therapeutic anatomical target. The stimulation parameters used to test the device and its relationship to each patient's anatomy in the operating room are not suitable as a guide for subsequent therapy. The nature of the anatomical relationship between the electrode(s) and the device is modified by the processes of wound granulation and healing so that the impedance characteristics and the exact anatomical relationship of the electrode to the target neurological tissue change during the post-operative period. As with other neuro-modulatory devices, the baroloop device is tested in the operating room, but the therapeutic stimulation delivered by the device is titrated only after ca. 2-3 weeks of healing has occurred. The intra-operative stimulation characteristics are not used to guide the titration to therapeutic effect - the device is tested in the operating room to make sure that it is operational, and the actual titration of stimulation to modify blood pressure will begin only after a period of post-surgical healing.

WARNING: Be aware of severe side effects, such as profound bradycardia.

If a severe side effect occurs (including severe bradycardia), stimulation must be stopped immediately, and appropriate corrective actions taken.

Any stimulation-related effects (blood pressure decrease, heart rate decrease, or any other possible response due to stimulation) should be recorded in the study Case Report Forms.

After intraoperative impedance, self-test and stimulation testing, set the IPG in shelf-mode by selecting 'Activate Shelf Mode' in the status dropdown menu on the Programmer screen.

WARNING: The IPG must be in INACTIVE MODE after implantation during the recovery from surgery.

4.23. 14-Day Follow-up Visit (+2 / -3 days)

- Clinical assessment of the subject;
- Physical examination;
- Changes of medication regimen;
- Review and assessment of adverse events;
- Office cuff blood pressure; and
- Initial testing and titration of stimulation to achieve up to a 20% reduction in systolic blood pressure or age-adjusted 2018 ESC/ESH treatment target office blood pressure (OBP), whichever blood pressure achieved during stimulation is lower.

N.B.:

1. If the patient is not judged to be ready for a first titration on day 14, the patient may return on or before day 21 for the first titration.
2. The first titration of blood pressure using baroloop stimulation (not earlier than 14 days after surgery when wound healing is complete) will be followed by a brief, one day hospitalization to observe the initial response to baroloop therapy.

